Protocol title: A pilot study of oxidative pathways in MS fatigue

Document Date: 10/12/2016

Version: 4

NCT: 02804594

PI: [name]., PhD
Professor of Clinical Neurology and Pediatrics
UCSF MS Center
Neuroscience Building
[name]
[name]

Protocol title: A pilot study of oxidative pathways in MS fatigue

PI: [name]., PhD
Professor of Clinical Neurology and Pediatrics
UCSF MS Center
Neuroscience Building
[name]
[name]

8. Statistical consideration and analysis plan

8.1 Statistical plan for specific aim 1- To test the tolerability and safety of NAC therapy (1250 mg three times a day) compared to placebo for 4 weeks to treat progressive MS fatigue.

Study Subjects: Target population- Adult patients with progressive MS and fatigue seen at UCSF.

The safety outcome will be analyzed by including all subjects who have received at least one dose of study medication. Participants will be analyzed according to the actual treatment received. The assessment of safety will be based on the frequency of adverse events.

The primary efficacy analysis will be done as an intent-to-treat analysis. Consequently, all randomized participants will participate in the analysis as allocated to NAC or placebo.

8.2 Statistical plan for specific aim 2- To obtain preliminary data on changes in fatigue levels and oxidative pathway biomarkers on NAC therapy in subjects with progressive MS fatigue.

In an intent-to-treat analysis, using Student t-test, the mean change in MFIS score from the baseline to week 4 will be compared between the NAC and placebo groups. The per-protocol secondary analysis will take into account treatment regimen. We will use similar models to compare the changes in brain GSH concentration and blood GSH/GSSG ratio, FSS, NeuroQOL fatigue item bank, 9-hole peg test, 25-foot timed ambulation, and Symbol Digit Modalities Test (SDMT) at the baseline and week fourth between the NAC and placebo groups.

Because there is a possibility for imbalance in the baseline values of potential confounding factors (such as EDSS and depression), an a priori secondary analysis is planned. To assess the effectiveness of NAC vs. placebo, we will use a linear regression model, comparing the mean change in MFIS score from the baseline to week 4, adjusting the models for the baseline EDSS and HADS scores.

We will use the same models to analyze the change in the severity of fatigue as measured by MFIS and FSS between week 4 (the end of study drug administration period) and week 6 (2 weeks after patients have been off study drug).

Because of the exploratory nature of these analyses, we will not correct our models for multiple comparison testing. Statistical analyses will be performed by a biostatistician from UCSF biostatistics department blinded to treatment assignment.

Sample size calculation: There are no available data to base power calculation for this aim as such a study has never been performed prior. We will use the data generated for this aim to design future studies.

Primary efficacy endpoint: The primary efficacy analysis will be done as an intent-to-treat analysis. Consequently, all randomized participants will participate in the analysis as allocated to NAC or placebo. Using Student t-test, the mean change in MFIS score from the baseline to week 4 will be compared between the NAC and placebo groups. The per-protocol secondary analysis will take in account treatment regimen.

MFIS consists of 21 items with a total score range of 0 to 84 (higher scores indicate worse fatigue). As the primary efficacy endpoint of the trial, we will compare the mean change in total MFIS score from baseline to week 4 visit between intervention and placebo groups.

Secondary efficacy endpoints (differences between treatment groups):

- Per protocol analysis for changes in MFIS from screening /baseline to week 4.
- MFIS subscales changes between screen/baseline and week 4.
- Change in FSS score from baseline to week 4.
- Change in NeuroQOL fatigue item bank score from baseline to week 4.
- Change in 9-HPT score from baseline to week 4.
- Change in 25-FTW from baseline to week 4.
- Change in SDMT score from baseline to week 4.
- Changes in MFIS and FSS between week 4 and 6.

8.3 Statistical plan for specific aim 3- To determine if fatigue severity is associated with baseline spectroscopy and oxidative pathway markers in patients with progressive MS.

We will examine the correlation between biomarkers (spectroscopy and blood oxidation metabolites) and fatigue (MFIS) at baseline. We will use a linear regression model with MFIS score (or its change) as the outcome and the spectroscopy and metabolites as the predictors (in

separate models). Using data obtained from the control subjects (patients with progressive MS and fatigue severity as measured by MFIS<38) we will also perform a case-control analysis (e.g. logistic regression with being fatigued or non-fatigued as the outcome and spectroscopy or blood metabolites as predictors).

Study variables

Demographic variables: Age, sex, self-reported race/ethnicity (based on the National Institute of Health classification), education (in years) and occupation will be recorded at the screening visit. Because the severity of fatigue may fluctuate during the day and based on the ambient temperature, the time of the visit and the outside temperature will also be recorded.

Baseline MS-related information: Years since disease onset, type of MS (primary versus secondary progressive (per medical records), Expanded Disability Status Scale (EDSS) (obtained at screening visit by the examining physician), and 25-foot timed walk (25-FTW), 9-hole peg test (9-HPT) and Single Digit Modalities test (SDMT) (obtained by a trained technician at screening, baseline and week 4).

Fatigue: MFIS and FSS (questionnaires filled by patients after receiving appropriate instructions from study staff, see appendix) at screening, baseline, week 4 (last study drug dose), and week 6 (2 weeks after stopping study drug).

Depression: Hospital Anxiety and Depression Scale (HADS) depression subscale (questionnaires filled by patients after receiving appropriate instructions from a study staff, see appendix) at screening and baseline.

Quality of life: NINDS NeuroQOL fatigue item bank (questionnaires filled by patients after receiving appropriate instructions from study staff, see appendix) at the screening, baseline and week 4.

Safety laboratory assessment: At screening, CBC and differential, creatinine, AST, ALT, urine analysis and urine pregnancy test will be obtained. At week 4, only creatinine, urine pregnancy test, AST and ALT will be measured.

Research laboratory assessment: Plasma level of reduced glutathione (GSH) and oxidized glutathione (GSSG) baseline and at 4 week visit for patients who enter treatment phase, and baseline research samples will be analyzed for patients who are controls in the study

Conventional MRI sequences: The MR experiments will be performed on the GE 7T research scanner in the Surbeck Laboratory using a 32-channel phased array head coil. The 60-minute MR protocol will include standard imaging sequences with calibration scans (3-plane localizer, coil sensitivity maps), gradient recalled-echo, T1-weighted and T2-weighted images, and multiband DWI. Higher order shimming will be performed prior to the spectral data acquisitions. The volume of interest for 3D short TE MRSI will be prescribed to have full coverage of the thalamus that will enable to measure metabolite levels (such as Cho, Cr, NAA, Glutamate,

Glutamine, mI, and GSH) in deep grey matter and surrounding normal appearing white matter. GSH-edited MRS will be acquired as well to provide unobstructed detection of GSH in the selected of regions of interest.

Data collection:

1) Blood samples from participating patients at the baseline and week 4 visits will be collected and analyzed for various metabolites on the oxidative pathway including GSH, GSSG, and response ratio for GSH, and GSSG.

2) 7T MR spectroscopy at the baseline and 4 week visits will be obtained and analyzed for concentrations of N-acetyl-aspartate (NAA), glutamate (Glu), glutathione, myo-inositol (mI), creatine (Cr), and choline (Cho) over the region of interest (ROI) region and concentrations of NAA, Glu, glutathione, mI, Cr, and Cho from normal-appearing white-matter areas within the ROI region.

Power considerations: There are no available data to base power calculation for this exploratory aim as such a study has never been performed prior. We will use the data generated for this Aim to design future studies.

9.Data collection, management and quality assurance

We will use Redcap (<http://project-redcap.org/>), a secure web application for building online databases, as the trial data management software. The demographic and baseline information will be entered directly from the medical records by study coordinator into the study CRF. The study manger will review CRFs for completeness and enter into Redcap database. UCSF research fellow ([name]) will double check the data entered into Redcap for accuracy.

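### Baseline MFIS is collected but is a covariate in neither the primary t-test nor the adjusted regression, so a modest gain in precision is usually given up

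*Combined protocol and SAP*

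**What the plan says.** Under Primary efficacy endpoint in Section 8.2, the main comparison has no covariates: "Using Student t-test, the mean change in MFIS score from the baseline to week 4 will be compared between the NAC and placebo groups".

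Section 8.2 also plans an a priori secondary analysis because "there is a possibility for imbalance in the baseline values of potential confounding factors (such as EDSS and depression"; it is a linear regression "comparing the mean change in MFIS score from the baseline to week 4, adjusting the models for the baseline EDSS and HADS scores". The wording that introduces the confounders offers EDSS and depression as examples, but the sentence that defines the model lists only those two covariates.

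The t-test approach is extended to brain GSH, the blood GSH/GSSG ratio, FSS, NeuroQOL fatigue, 9-HPT, 25-FTW and SDMT. For the off-drug period the plan says "We will use the same models to analyze the change in the severity of fatigue as measured by MFIS and FSS" from week 4 to week 6.

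The missing covariate is available. Under Study variables, MFIS and FSS are completed "at screening, baseline, week 4 (last study drug dose), and week 6 (2 weeks after stopping study drug". The blood markers also have their own baseline: "Blood samples from participating patients at the baseline and week 4 visits will be collected and analyzed for various metabolites on the oxidative pathway".

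**The concern.** A change score uses baseline MFIS, but with its slope fixed at 1. When week 4 MFIS correlates with baseline at rho below 1 and the SDs are equal, the best slope is rho, so the change score over-corrects. If one arm happens to start D points worse, the estimated difference moves by (1−rho)D in that arm's favour. Averaged over randomisations this cancels, so there is no bias. It appears instead as extra variance, already counted in the t-test's standard error. Lost precision and sensitivity to baseline imbalance are therefore one loss, not two.

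Two things make it worth raising. The adjusted analysis exists to handle baseline imbalance, yet it does not adjust for the baseline of the outcome itself. And Section 8.2 says of this aim "We will use the data generated for this aim to design future studies", so the effect estimate and its interval are a main product of the trial.

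**Working it through.** **Inputs.** From the documents: the two models, the MFIS visit schedule, and a control group defined as "patients with progressive MS and fatigue severity as measured by MFIS<38". Not in the documents: sample size, SD, treatment effect and rho. Assumed: SD 15 at both visits, true difference 10, rho from 0.3 to 0.9, and mainly 15 per arm. Entry at MFIS of 38 or more is inferred from the control cut-off. For that case the unrestricted population is taken as normal with mean 45. The plan states no figure that could be reproduced.

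**1. Large-sample variance, any entry score.** With s0 and s1 the SDs at baseline and week 4, the variance of the effect is proportional to
- change score: s0² + s1² − 2·rho·s0·s1
- ANCOVA: s1²(1 − rho²)

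The difference is (s0 − rho·s1)², never negative and zero when s0 = rho·s1. With equal SDs the ratio ANCOVA/t-test is (1 − rho²)/[2(1 − rho)] = (1 + rho)/2.

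**2. Large-sample variance, restricted entry.** Cutting a normal (mean 45, SD 15) at 38 leaves a fraction k = 0.477 of the baseline variance, so the baseline SD is 15·√0.477 = 10.4. With rho the correlation before restriction, the ratio is (1 − rho²)/[(1 − rho²) + k(1 − rho)²]. At rho 0.5 this is 0.75/(0.75 + 0.477·0.25) = 0.86.

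**3. Small samples.** Simulation (20,000 trials per setting) includes the cost of estimating the slope. Variance ratio ANCOVA/t-test:

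| Setting | rho 0.3 | 0.5 | 0.7 | 0.9 |
|---|---|---|---|---|
| Large sample, any entry | 0.65 | 0.75 | 0.85 | 0.95 |
| 15 per arm, any entry | 0.67 | 0.78 | 0.88 | 0.99 |
| Large sample, restricted | 0.80 | 0.86 | 0.92 | 0.975 |
| 30 per arm, restricted | 0.81 | 0.87 | 0.94 | 0.99 |
| 15 per arm, restricted | 0.82 | 0.89 | 0.95 | 1.01 |
| 10 per arm, restricted | 0.85 | 0.92 | 0.99 | 1.04 |
| 5 per arm, restricted | 0.94 | 1.02 | 1.07 | 1.14 |

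Power at 15 per arm with restricted entry, t-test then ANCOVA: 38% and 44%, 47% and 51%, 66% and 68%, 98% and 98% at rho 0.3, 0.5, 0.7 and 0.9.

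**4. The same loss seen as imbalance.** A one-standard-error baseline difference is SD·√(2/n). At 15 per arm that is 10.4·√(2/15) = 3.8 points (restricted) or 15·√(2/15) = 5.5 points (any entry). Multiplied by (1 − rho), the t-test estimate shifts by 1.9 or 2.7 points at rho 0.5, 1.1 or 1.6 at 0.7, and 0.4 or 0.5 at 0.9. For scale, the restricted t-test standard error at rho 0.5 is 15·√[(0.75 + 0.477·0.25)·2/15] = 5.1.

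**5. Does the EDSS/HADS model already deal with it?** Assume EDSS correlates 0.2 to 0.4 and HADS 0.3 to 0.6 with baseline MFIS, and that they predict nothing further. If they are also unrelated to each other given baseline MFIS, the share of the shift removed is S/(1 + S). Here S is the sum of r²/(1 − r²) over the two covariates, multiplied by k under restricted entry.
- Weakest, restricted: S = 0.477·(0.04/0.96 + 0.09/0.91) = 0.067, so 6%.
- Strongest, any entry: S = 0.16/0.84 + 0.36/0.64 = 0.753, so 43%.

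At 15 per arm and rho 0.5 or 0.7, the simulated variance of the planned model is 0.97 to 1.07 times the t-test's. Adding baseline MFIS brings it to 0.81 to 0.98 of the planned model's variance. With restricted entry that is still 0.97 to 1.04 of the t-test's.

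**The case against.** The strongest reply is that nothing here is an error. The t-test is valid, the change score already uses baseline MFIS, the analyses are labelled exploratory, and no stated decision rule rests on the result. Both MFIS values are recorded, so an ANCOVA estimate, the SDs and rho can be computed for planning whichever analysis is called primary. All of this stands, and it caps the severity. It does not remove the reason to prespecify: a covariate chosen after the data are seen carries less weight.

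The second reply is that the benefit rests on unknown inputs and can be negative. This also stands. With restricted entry and rho 0.9, power falls from 55% to 50% at 5 per arm and from 89% to 88% at 10 per arm. In the other direction, if eligibility used the screening score and the covariate is a separate baseline score, restriction would bite less and the gain would be somewhat larger.

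Third, adding baseline MFIS to the EDSS/HADS model hardly improves on the existing t-test when entry is restricted. That is correct, and it is why baseline MFIS alone is preferred for the primary model. Fourth, the calculations cover MFIS only. For the other endpoints the argument is the same, but its size has not been worked out and would be small where baseline and week 4 correlate highly.

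**Conclusion.** The concern holds. Baseline MFIS is a covariate in no treatment comparison, and the text leaves no doubt about that. The consequence is a modest loss of precision in most plausible settings. At 15 per arm, using baseline MFIS would cut the variance by about 22% (any entry) or 11% (restricted entry) at rho 0.5, and by 12% or 5% at rho 0.7. There is nothing to gain, and possibly a little to lose, at rho near 0.9 or about 5 per arm. These sizes depend on the assumed SD, rho, sample size and entry rule; the omission does not. This is a worthwhile, inexpensive improvement to a valid plan, not a flaw that threatens its conclusions.

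**What to change.** - Make the primary intention-to-treat analysis an ANCOVA of week 4 MFIS (or its change; the treatment effect is the same) on arm and baseline MFIS alone, reported with a 95% confidence interval.
- State which pre-treatment MFIS value is the covariate, since it is measured at both screening and baseline and the list of secondary endpoints in Section 8.2 refers to either.
- Add baseline MFIS to the EDSS/HADS regression and keep that model secondary.
- For the other baseline-to-week-4 endpoints, adjust for each endpoint's own pre-treatment value.
- For the week 4 to week 6 changes, do not use the week 4 value as the baseline covariate, because it is measured after randomisation.
- Keep the Student t-test as a sensitivity analysis.

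The cost is SAP wording and one residual degree of freedom. No new data are needed.

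### Does the plan need a week 6 comparison of the arms against baseline, beyond the planned week 4 to week 6 change in MFIS and FSS?

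*Combined protocol and SAP*

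**What the plan says.** The Fatigue entry under Study variables has MFIS and FSS completed "at screening, baseline, week 4 (last study drug dose), and week 6 (2 weeks after stopping study drug"). A week 6 score referred to baseline could therefore be computed.

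In section 8.2 the primary contrast is change from baseline to week 4: "we will compare the mean change in total MFIS score from baseline to week 4 visit between intervention and placebo groups". The method is given as "using Student t-test, the mean change in MFIS score from the baseline to week 4 will be compared between the NAC and placebo groups", with a secondary linear regression adjusted for baseline EDSS and HADS.

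The list headed "Secondary efficacy endpoints (differences between treatment groups") contains both "Change in FSS score from baseline to week 4" and "Changes in MFIS and FSS between week 4 and 6". The last of these is the only listed endpoint that uses week 6, and the text above the list applies the same models to it: "We will use the same models to analyze the change in the severity of fatigue as measured by MFIS and FSS between week 4" and week 6. Section 8.2 calls these analyses exploratory, makes no multiplicity correction, and says of the results: "We will use the data generated for this aim to design future studies".

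**The concern.** Week 4 is measured after randomisation and on drug. A contrast that starts there measures what happens on withdrawal, and on its own it says nothing about whether there was an effect to lose. A zero can mean no effect at any time or full persistence.

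Two further points seem to add weight. The week 4 score enters the two planned contrasts with opposite signs, so a chance benefit at week 4 could be followed by an apparent loss off drug and be taken as confirmation that the drug worked. Also, a confidence interval for the week 6 difference against baseline needs the covariance of the two changes, which two separate analyses do not supply. If the size and precision of the off-drug effect matter for designing the next trial, the plan would seem to leave them out.

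**Working it through.** The documents give no SD, visit correlation, arm size or power figure, so there is no stated figure to reproduce. Everything numerical below rests on assumptions.

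**1. Can the planned pair tell the cases apart?** Let d4 be the arm difference in change from baseline to week 4, and d6 the same to week 6. The plan estimates d4 and d6 − d4. Take an assumed true week 4 effect of −8 MFIS points.

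| Case | d4 (planned) | d6 − d4 (planned) | d6 |
|---|---|---|---|
| Never worked | 0 | 0 | 0 |
| Full persistence | −8 | 0 | −8 |
| Half lost | −8 | +4 | −4 |
| Fully lost | −8 | +8 | 0 |

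Each case has its own planned pair. The week 6 contrast alone has the mirror ambiguity: it is zero both for never worked and for fully lost. Since d6 = d4 + (d6 − d4), the two pairs carry the same information about the point estimates when the same participants are in both analyses.

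**2. Is the planned test valid?** It compares a change score between randomised arms. In simulation with no true effect (normal data, 10 per arm, 200,000 trials, settings A, B and D below), it rejected at a two-sided rate of 0.050 each time.

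**3. Dependence between the two planned estimates.** Assume equal SDs at the three visits and correlations a (baseline–week 4), b (week 4–week 6) and c (baseline–week 6). In SD² units:

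- Var(week 4 − baseline) = 2(1 − a)
- Var(week 6 − week 4) = 2(1 − b)
- Cov = a + b − c − 1
- correlation = Cov / √[2(1 − a) · 2(1 − b)]

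| Setting | a / b / c | Cov | Correlation |
|---|---|---|---|
| A | 0.7 / 0.7 / 0.7 | −0.30 | −0.30/0.600 = −0.50 |
| B | 0.7 / 0.8 / 0.7 | −0.20 | −0.20/0.490 = −0.41 |
| C | 0.7 / 0.8 / 0.6 | −0.10 | −0.10/0.490 = −0.20 |
| D | 0.7 / 0.8 / 0.56 | −0.06 | −0.06/0.490 = −0.12 |
| E | 0.7 / 0.8 / 0.5 | 0 | 0 |
| F | 0.8 / 0.9 / 0.65 | +0.05 | +0.05/0.283 = +0.18 |

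Sharing the week 4 score with opposite sign does not by itself make the correlation negative. The sign depends on how quickly correlation falls between visits.

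**4. Would a baseline-adjusted week 6 effect avoid the dependence?** Its correlation with the baseline-adjusted week 4 effect is (b − ac) / √[(1 − a²)(1 − c²)]:

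- A: 0.21/0.51 = +0.41
- B: 0.31/0.51 = +0.61
- C: 0.38/0.571 = +0.67
- D: 0.408/0.592 = +0.69

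Now suppose there is no true effect and a chance 6-point benefit at week 4. The expected apparent loss in the planned contrast is 6 × |Cov| / [2(1 − a)]. The expected apparent persistence in the adjusted week 6 effect is 6 × (b − ac)/(1 − a²).

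| Setting | Apparent loss, planned contrast | Apparent persistence, week 6 effect |
|---|---|---|
| A | 3.0 | 2.5 |
| B | 2.0 | 3.6 |
| C | 1.0 | 4.5 |
| D | 0.6 | 4.8 |

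In three of the four settings the week 6 effect carries over more of a chance week 4 result than the planned contrast does.

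**5. The interval for d6.** Adding the two variances without the covariance would overstate the standard error by √{[2(1 − a) + 2(1 − b)] / [2(1 − c)]} − 1, which is 41%, 29%, 12% and 7% in A to D. With SD 15, 10 per arm and setting A, the 95% half-width is 2.101 × 15 × √(0.60 × 2/10) = 10.9 points, against 2.101 × 15 × √(1.20 × 2/10) = 15.4 without the covariance. This is the cost of an error that the plan does not propose. Section 8.2 nowhere combines the two analyses in this way, and anyone wanting d6 can take the week 6 minus baseline change directly from the collected scores.

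**The case for a change.** The best case for the concern is that the reading of the text is right and the remedy is cheap. Week 6 is used only against week 4, and baseline MFIS or FSS is not even a covariate in that analysis. The plan gives no interval for the effect two weeks off drug. In a pilot meant to inform later trials, that estimate could be useful, and it needs one supportive model on data already held.

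The factual part stands, and so does the usefulness of the estimate. It does not follow that the plan is deficient. Aim 2 asks about changes during NAC therapy. The week 6 visit adds a question about withdrawal, and the week 4 to week 6 change answers that directly. The off-drug effect against baseline is a different quantity, which the plan does not set out to estimate. The plan also nowhere treats a loss off drug as independent confirmation of benefit. The missing interval is not particular to week 6, because the supplied text names no confidence interval for any endpoint.

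**Conclusion.** The concern does not hold. Followed as written, the plan gives a valid between-arm test of change after withdrawal, alongside the baseline to week 4 comparison of the same two scales. Together these distinguish no effect, persistence and loss. The primary analysis is unaffected. Dependence between the two planned estimates ranges from −0.50 to +0.18 over the six assumed settings, and replacing one of them with a baseline-adjusted week 6 effect would bring its own dependence of +0.41 to +0.69 (settings A to D).

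What remains is a preference for one more supportive estimate on an exploratory pilot endpoint. The magnitudes assume equal SDs across visits, the listed correlations and, for the half-widths, SD 15 with 10 per arm. The identity d6 = d4 + (d6 − d4) needs the same participants in both estimates, so losses between week 4 and week 6 would make it approximate. The supplied document begins at section 8, so this conclusion covers only that text.

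### No planned treatment comparison adjusts for pre-treatment MFIS, although two such scores are collected, and the start value of the per-protocol and subscale MFIS changes is undefined

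*Combined protocol and SAP*

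**What the plan says.** The Fatigue entry under Study variables has MFIS completed "at screening, baseline, week 4 (last study drug dose), and week 6 (2 weeks after stopping study drug"), so two scores precede treatment.

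Section 8.2 states the primary analysis as a Student t-test in which "the mean change in MFIS score from the baseline to week 4 will be compared between the NAC and placebo groups". The primary efficacy endpoint paragraph repeats this for the total score: "we will compare the mean change in total MFIS score from baseline to week 4 visit between intervention and placebo groups". The a priori secondary regression compares the same change, "adjusting the models for the baseline EDSS and HADS scores"; pre-treatment MFIS is not among the covariates.

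In the list of secondary efficacy endpoints, two bullets use a different start:

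- "Per protocol analysis for changes in MFIS from screening /baseline to week 4"
- "MFIS subscales changes between screen/baseline and week 4"

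The other week 4 bullets (FSS, NeuroQOL, 9-HPT, 25-FTW, SDMT) name baseline alone, for example "Change in FSS score from baseline to week 4". Under Study variables these measures are also collected at screening, so the slash does not simply mark outcomes that have two pre-treatment readings.

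**The concern.** There are two separate matters.

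**Precision.** A t-test on change subtracts the whole of the baseline score, including its visit-specific noise. ANCOVA subtracts only the part that predicts week 4. The plan itself expects fatigue to vary with time of day and ambient temperature, so a single reading is likely to be noisy. The stated reason for the secondary regression is possible baseline imbalance, yet it omits the variable most directly related to the outcome.

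**Start value.** A per-protocol result should differ from the intent-to-treat result only in who is analysed. Subscale changes add up to the total change only if all are measured from the same score. The slash could mean the screening score, the baseline score, their mean, whichever is available, or simply the pre-treatment value. Nothing in the text chooses between these, so the choice could be made after the data are seen, in a plan that makes no multiplicity correction.

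**Working it through.** The documents state no sample size, SD, effect size or correlation, so there is no figure of the plan's to reproduce. Every correlation below is an assumption and refers to the patients enrolled.

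Notation: S, B and W4 are MFIS at screening, baseline and week 4. Variances are set to 1 at each visit, and r_SB, r_B4 and r_S4 are the pairwise correlations.

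**1. Adjusting for baseline MFIS.**

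- t-test on change: Var(W4 − B) = 2(1 − r), with r = r_B4.
- ANCOVA on B: residual variance 1 − r².
- Ratio: (1 − r²) / [2(1 − r)] = (1 + r)/2.

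ANCOVA uses the best-fitting slope, whereas the change score fixes the slope at 1. Apart from the degree of freedom for the slope, the ratio therefore cannot exceed 1.

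**2. Adding screening MFIS as a separate covariate, all correlations equal to r.**

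- Residual variance: 1 − 2r²/(1 + r).
- Ratio to the t-test: [1 − 2r²/(1 + r)] / [2(1 − r)].

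| r | t-test on change | ANCOVA, baseline | Ratio | ANCOVA, both scores | Ratio |
|---|---|---|---|---|---|
| 0.5 | 1.00 | 0.75 | 0.75 | 0.667 | 0.67 |
| 0.6 | 0.80 | 0.64 | 0.80 | 0.550 | 0.69 |
| 0.7 | 0.60 | 0.51 | 0.85 | 0.424 | 0.71 |
| 0.8 | 0.40 | 0.36 | 0.90 | 0.289 | 0.72 |

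For baseline MFIS alone, ratios of 0.75 to 0.90 are worth 1/0.75 = 1.33 to 1/0.90 = 1.11 times as many patients under the t-test. At r = 0.3 and r = 0.9 the single-covariate ratios are 0.65 and 0.95.

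**3. Unequal correlations: separate covariates against an average.** With both scores entered separately, the residual variance is 1 − r_B4² − (r_S4 − r_SB·r_B4)²/(1 − r_SB²). This never exceeds 1 − r_B4². Take (r_SB, r_B4, r_S4) = (0.8, 0.8, 0.64):

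- Separate covariates: r_S4 − r_SB·r_B4 = 0.64 − 0.64 = 0, so the variance stays at 0.36. The ratio to baseline-only ANCOVA is 1.00.
- Change from the mean of S and B: 1 + (1 + 0.8)/2 − 0.8 − 0.64 = 0.46, against 2(1 − 0.8) = 0.40. The ratio is 1.15.
- ANCOVA on the mean of S and B: squared correlation with W4 = 0.72²/0.90 = 0.576, residual 0.424, against 0.36. The ratio is 1.18.

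Averaging helps a change-score t-test only if r_B4 − r_S4 < (1 − r_SB)/2. Here 0.16 is not below 0.10.

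**4. Regression to the mean, if screening set entry.** Controls are defined by MFIS below 38. Suppose treated patients had to score 38 or more at screening (assumed), from a population with mean 38 to 45 and SD 16, with r between 0.6 and 0.8. The expected fall from screening to the next visit is (1 − r) × (truncated mean − population mean):

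- Largest: 0.4 × 12.8 = 5.1 points (mean 38, r = 0.6).
- Smallest: 0.2 × 8.7 = 1.7 points (mean 45, r = 0.8).

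A start value averaged over both visits would keep half of this, 0.9 to 2.6 points. The baseline visit alone would keep none. Under randomization the expected fall is the same in both arms.

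**The case against.** The slash may be loose wording for the single pre-treatment value. Section 8.2 introduces the per-protocol analysis straight after the baseline-to-week-4 t-test and says only that it takes treatment regimen into account. The plan uses baseline loosely elsewhere: it adjusts for baseline EDSS, but Study variables has EDSS obtained at screening. The text available begins at section 8, so a definition could sit in the eligibility or visit-schedule sections. This stands. A reader might infer that the per-protocol and subscale results are not comparable with the primary, but no sentence says that they use a different score.

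Change from the baseline visit is a valid endpoint, stated consistently, in a pilot that calls its analyses exploratory and makes no power claim. That also stands: the t-test is less precise than it could be, not wrong.

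A reader might infer that averaging the two pre-treatment scores would sharpen the primary at no cost. With equal correlations it would lower the change-score variance by 25%, but the documents give neither the correlations nor the screening-to-baseline interval, and step 3 shows that it can lose precision. If screening set entry, the average would also bring regression to the mean into the start value.

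A reader might also infer that regression to the mean biases the treatment effect. It would not. It affects within-arm changes, and the endpoints are differences between randomized groups. The entry rule behind it is itself an assumption.

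Finally, moving from a t-test to ANCOVA changes the primary estimator and is more than a wording edit. That is correct and is reflected in the cost below.

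**Conclusion.** The point holds as an avoidable loss of precision together with a wording gap. It is not a flaw that invalidates the primary comparison.

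For an assumed baseline-to-week-4 correlation of 0.5 to 0.8 and equal variances at the two visits, adjusting for baseline MFIS lowers the variance of the primary comparison by 10% to 25%. Screening MFIS as a second, separate covariate makes the reduction 28% to 33% if all visit correlations are equal. If screening adds nothing beyond baseline, it costs one degree of freedom. These figures compare ANCOVA with the unadjusted t-test. The gain over the regression on EDSS and HADS would depend on how those scores relate to MFIS, which the documents do not give.

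The start value of the per-protocol and subscale changes is undefined in this text. Whether it actually differs from the primary's cannot be settled from the documents.

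**What to change.** 1. State that the baseline-visit MFIS is the start value in the primary, per-protocol, subscale and regression analyses, and replace both slash phrases in the secondary endpoint list accordingly.
2. Analyse week 4 MFIS, or its change from baseline, by ANCOVA with treatment and baseline MFIS in the model. Once baseline MFIS is a covariate, the two outcomes give the same treatment estimate. Add baseline MFIS to the EDSS and HADS regression as well.
3. Optionally, enter screening MFIS as a second, separate covariate. Do not average it with the baseline score.

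The first item is a wording change. The second alters the primary estimator, so it needs a dated SAP amendment before treatment codes are released; the t-test can be kept as a supporting analysis. Both scores are already collected, so no visits, patients or measurements are added. The statistical cost is one degree of freedom per covariate.
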